11.3 Data handling and analysis

A data management SOP will be followed. A web-based database will be programmed by Sealed Envelope. The software is Sealed Envelope's own software application with an underlying MySQL database for storage. It has been used successfully in other trials over the last five years.

The web-based database will include the following:

- All information recorded in the paper CRF
- Randomisation records
- EQ-5D, CAT and SGRQ questionnaires
- Diary card

The system will also have the following attributes:

- Password protected user accounts for Delegated staff at each site.
- Single data entry with validation checks and source data verification against the data in the database.
- Have the ability to edit data and view history of edits. Only authorised delegated members of staff at each site will be able to edit the data from that site.
- Have the ability to add queries to CRFs to assist with follow-up of missing data or other issues.
- Full audit log of all changes to data
- The delegated research staff at both sites and the statisticians in Cambridge will have read-only access to the electronic data set (back end access) to download whenever required for data

cleaning and/or analysis purposes. Queries can be raised and will be addressed by the authorised delegated members of staff at site.

- An audit trail will be maintained of any change or correction to the case report form or the electronic database. Data will be generated, recorded and reported in compliance with the protocol and with Good Clinical Practice. Free text variables will also be allowed to describe, for example, deviations from the protocol. These will also be recorded on the protocol deviation log.
- The CRFs are designed for ease of use and to minimise cross-validation errors. Nevertheless, data cleaning and monitoring will be conducted by the trial manager and statistician during and at the end of the trial. It will be possible to check patient notes with any queries that arise.
- Data will not be double entered.
- Data entries will be checked to ensure they fall within the normal parameters at the time of entry- data will also be reviewed by the statistician and members of the steering committee for other queries.
- The Authorised delegated members of staff at both sites will complete data entry in the paper CRF at the time of seeing the patient. This data will then be entered onto the online database. Site staff may insert new records and browse records they have previously entered, but will not be able to access records of patients from the other trial site.
- Data entered via the website will not contain personal identifiers.
- Each patient will be given a unique number, which will be linked to a paper record of the participants' names and addresses. This will only be accessible by trial personnel seeing patients at the study site. Any patient-identifiable data will be stored securely and separately from anonymised documents at each site, and will not be entered onto the electronic database.
- The database will also be accessed centrally by the study statistician and the steering committee (on a read only basis) and analysed to assess recruitment and retention levels and for data cleaning according to specified SOPs developed by the research team.
- Data analysis for the trial will be done by the trial Statistician who is independent to the person entering the data on to the database.
- All data collected will be in adherence to Data Protection Act 1998 , as well as IMPERIAL COLLEGE LONDON Information Security Policy and Trust Information Governance Polices. The data will be stored in a highly secure data centre owned and operated by Rackspace in the UK (www.rackspace.co.uk). The data centre is audited annually under the SAS70 accreditation system. Backup is daily to tape on-site (2 week retention) and hourly offsite to a failover server with full disk encryption held at Sealed Envelope's offices. In the event of disaster at the main data centre online operations can be switched to the failover server.

11.4 Record keeping and archiving

Archiving will be authorised by the Sponsor following submission of the end of study report.

- Site Files and Consent Forms will be securely stored with access restricted to trial authorised persons only at participating sites.
- CRF will be securely stored with access restricted to trial authorised persons only at participating sites as a hard (paper) copy.

- All essential documents held at sites (e.g. CRF, Site Files and Consent forms) will be archived at site according to local trust policy. These documents will be archived for a minimum of 5 years after completion of the trial.
- The electronic trial database, which includes an electronic version of the CRF, will be stored electronically on the server of Sealed Envelope™. Authorised staff at the Dept of Respiratory Medicine at the ROYAL BROMPTON and Harefield NHS Foundation Trust, Dept of Clinical Sciences, as well as to the study statisticians ([name] and [name]) at the MRC Biostatistics Unit, Cambridge, will be able to access this data as needed. At the end of the analysis, the database will be securely transferred electronically (based on the secure processes Sealed Envelope have in place and the arrangements will be detailed in the data management SOP) to the Dept of Respiratory Medicine at the ROYAL BROMPTON and Harefield NHS Foundation Trust. Only Trial authorised persons will have access to the database.
- Chief Investigator is responsible for the secure archiving of essential trial documents within the TMF for the trial and the trial database as per their trust policy. All essential documents will be archived for a minimum of 5 years after completion of the trial.

Destruction of essential documents will require authorisation from the Sponsor.

12 Statistical Considerations

[name] and [name] are the trial statisticians who will be responsible for all statistical aspects of the trial from design through to analysis and dissemination.

12.1 Outcomes

12.1.1 Primary outcome

The primary outcome will be the time in days to the first day of the next exacerbation following IMP start (at day 0, 14 days after the initial exacerbation), up to a maximum of 90 days. Exacerbation is defined fully below. Patients who do not suffer a recurrent exacerbation will be censored at the end of follow-up / time of drop-out.

The onset of the next (recurrent) exacerbation will be defined as **either**:

- 1) The first day of treatment with antibiotics and/or steroids for an exacerbation of COPD (HCU definition), **or**
- 2) The first of two or more consecutive days of increased respiratory symptoms recorded on the daily diary cards, either:
 - a. Two 'major' symptoms (increased dyspnoea, increased sputum volume, or increased sputum purulence), **or**
 - b. One 'major' and one 'minor' symptom (cold, wheeze/chest tightness, sore throat, cough or fever).

A recurrent exacerbation will only be diagnosed based on diary cards if there are a minimum of five symptom-free days after the end of the previous exacerbation.

The end of the first exacerbation will be defined as the first day of two consecutive symptom-free days.

12.1.2 Secondary outcomes

- Duration of the initial exacerbation (from point of retreatment V0) based on diary card symptoms. The exacerbation will be considered to have ended on the first of two consecutive symptom-free days.
- Treatment-related adverse events
- Exacerbation frequency (rate) during follow-up.
- Total number of antibiotic courses received during follow-up
- Rates of (re)admission/re-attendance to hospital during follow-up
- Changes in respiratory healthcare status, during follow-up, assessed using SGRQ and CAT. Changes in lung function during follow-up.
- Change in CRP during follow-up.
- Changes in bacterial resistance to ciprofloxacin as assessed by standard culture and sensitivity methods at trial beginning and end (in those patients in whom sputum is spontaneously expectorated)
- Change in bacterial load from trial beginning to end (in those patients in whom sputum is spontaneously expectorated)
- Cost-effectiveness will be assessed as part of a future study (WP5)

12.2 Sample size and recruitment

12.2.1 Sample size calculation

Over the two centres, based on HES data, we anticipate that a total of 218 hospital admission or ambulatory exacerbations will be identified over the 18-month recruitment period (<http://www.hscic.gov.uk/hes>). Based on data from the London COPD Cohort, 33% of exacerbating patients have a CRP of 8 or above at 2 weeks. Furthermore, our pilot data suggest that of patients with CRP >8mg/L, at least 60% of patients report symptoms at day 14. Thus, assuming that 90% of eligible patients will agree to take part in the study, we expect $218/3 \approx 73$ patients eligible due to CRP level, $0.6(218-73) = 87$ eligible due to symptoms at day 14, and to randomise $0.9(73+87)=144$ patients in total.

Pilot data from our group suggests that at a level of CRP>10mg/l at 14 days, there will be 36% recurrent exacerbations within 50 days. Assuming a constant hazard of exacerbation this translates to around a 55% recurrent exacerbation rate at 90 days. A similar proportion of recurrent exacerbations are seen in the London COPD cohort (for both CRP>10 and CRP<10). An observational database study by Roede et al. (2008) reported a hazard ratio of 0.62 when antibiotics were given in addition to usual treatment. Allowing for a 5% dropout, we will therefore have 80% power at a 5% two-sided significance level to detect a 22% absolute reduction in the proportion of exacerbations seen at 90 days (from 55% to 32%), using time-to-event (survival) methods. This is equivalent to detecting a hazard ratio of 0.48 over the follow-up period.

The recruitment period for this trial is estimated to be 18 months, requiring approximately 8 patients per month to be randomised across both sites.

12.3 Statistical analysis plan

12.3.1 Summary of baseline data and flow of patients

A CONSORT diagram will be produced to illustrate recruitment and flow of patients through the study. (<http://www.consort-statement.org/>)

The variables to be collected at day zero are:

- Bacterial load: If spontaneously expectorated, sputum samples will be collected and analysed to measure bacterial load in the lung. Concentrations will be log transformed and expressed as log₁₀ CFU (colony forming units)/ml. Collection of sputum is not a requirement for study entry and this will therefore form a subgroup analysis.
- CRP: Blood samples will be collected and analysed for CRP levels to measure presence of inflammation in the body. This is measured in milligrams per litre of blood (mg/L)
- Spirometry: A test used to measure lung function. Specifically the measurement of volume and flow of air inhaled and exhaled. The parameters measured will be the Forced vital capacity (FVC) and Forced expiratory volume (FEV) at 1 second. The FEV₁/FVC ratio and FEV₁ as a percentage of Predicted Normal value will be computed.
- SGRQ: This is a standardized self-completed questionnaire for measuring impaired health and perceived well-being ('quality of life') in airways disease. It has been designed to allow comparative measurements of health between patient populations and quantify changes in health following therapy.
- EQ5D: This is a standardised instrument for use as a measure of health outcome. It provides a simple descriptive profile and a single index value for health status. Health outcome at treatment end will be compared to baseline data to assess change in health status.
- CAT: This is a standardised self-completed symptom questionnaire
- Age and Gender
- Smoking status
- Self-reported exacerbation frequency in the previous year

Summary statistics for all baseline variables will be presented (mean, standard deviation, median, interquartile range for continuous variables, percentages for categorical variables), stratified by treatment group, site and presence of symptoms to assess baseline comparability. No formal statistical tests of these baseline comparisons will be made.

The flow of patients through the trial will be summarised in a CONSORT diagram, showing all exclusions including reasons for non-randomisation and drop-outs / lost to follow-up statistics. The CONSORT diagram will be stratified by randomised group.

12.3.2 Primary outcome analysis

The primary outcome is the time to the next exacerbation within the 90-day study period. This will be analysed using Cox proportional hazards regression and the estimated hazard ratio between the groups will be reported, along with its standard error. A log-rank test will be used to test the primary hypothesis. A Kaplan-Meier plot will be produced. Patients who do not suffer a recurrent exacerbation during follow-up will be treated as censored observations at their end of follow-up time. As analysis is intention to treat, non-compliers will be treated as belonging to the treatment group originally randomised to. Where patients withdraw from follow up, every effort will be made

to ascertain their primary outcome (i.e. date of next exacerbation OR exacerbation-free survival to 90 days) by telephone.

Analysis will be adjusted for a number of important baseline covariates including; sex, exacerbation phenotype, level of symptoms (CAT), levels of CRP, disease severity (FEV), baseline exacerbation frequency in previous year, hospital admission at initial exacerbation.

12.3.3 Secondary outcome analysis

Summary measures of the secondary endpoints will be presented (mean, standard deviation, median, interquartile range for continuous variables, percentages for categorical variables) by treatment group and for both baseline and end of trial follow-up visits. The percentage of missing data will be summarised.

- Time until resolution of first exacerbation will be compared between the active treatment and placebo groups, using a log-rank test. Cox regression analysis will also be conducted adjusting for important baseline covariates.
- The number of treatment-related adverse events will be analysed by using (over dispersed) Poisson regression or a suitable zero-inflated model and adjusted for treatment group and important baseline covariates.
- Exacerbation frequency: The rate of exacerbations experienced during the study period will be analysed by using (over dispersed) Poisson regression or a suitable zero-inflated model and adjusted for treatment group and important baseline covariates and with length of follow-up as an offset.
- Frequency of antibiotic courses: The rate of antibiotic courses received for patients in the active treatment and placebo groups will be compared using (over dispersed) Poisson regression or a suitable zero-inflated model adjusting for treatment group and important baseline covariates.
- The rate of hospital attendances during the study period will be analysed by using (over-dispersed) Poisson regression or a suitable zero-inflated model and adjusted for treatment group and important baseline covariates.
- Changes in respiratory healthcare status, assessed using SGRQ and CAT. SGRQ (score between 0 and 100) and CAT (score between 0 and 40) from baseline to day 90 will be modelled as a normally distributed random variable by using a suitable transformation (e.g. a Box-Cox like transformation to remove skewness and possible boundary effects). Any analysis will be adjusted for baseline scores, treatment, and other important baseline covariates. Repeated measures analysis will be used to assess treatment effects over time during the follow-up period.
- Lung function: Changes in FEV1, FEV1 as % predicted, and FEV1/FVC ratio and FVC at day 90 from day 0 will be modelled separately as continuous outcomes and assumed to be normally distributed (an appropriate transformation will be applied before analysis if required). Analyses will be adjusted for baseline values, treatment, and other important baseline covariates. Repeated measures analysis will be used to assess treatment effects over time during the follow-up period.
- Change in CRP from study entry to 90 days will be modelled as a normally distributed random variable by using a suitable transformation (e.g. a Box-Cox like transformation to remove skewness and possible boundary effects). Any analysis will be adjusted for baseline CRP, treatment, and other important baseline covariates. Repeated measures analysis will be used to assess treatment effects over time during the follow-up period.

- Resistance patterns (not resistant, resistant) will be analysed using logistic regression and adjusting for treatment group, baseline values and other important baseline covariates.
- The change in bacterial load from trial beginning to end will be analysed using multiple tobit regression and adjusting for baseline values and other relevant baseline covariates. Values below limits of detection will be treated as left censored observations in the tobit regression analysis.
- Adherence as assessed by pill counts. The number of pills taken over total number dispensed will be modelled using logistic regression (Binomial distribution with logit link). The difference in percent adherence will be assessed between treatment groups.
- Cost-effectiveness will be assessed as part of a future study (WP5)

This study is not powered to test these secondary outcomes – only the primary outcome. As such, analyses of the secondary outcomes will be hypothesis generating only.

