Objectives: The primary outcome will be the time to the next COPD exacerbation following targeted retreatment with the IMP or placebo.

Secondary endpoints will include duration of the initial exacerbation, adverse events, changes in lung function and health status, bacterial load and resistance, and hospital readmission.

Type of trial: Phase III, double-blind, randomised, placebo controlled, multicentre trial.

Trial design and methods: A 90 day, double-blind, randomised, placebo controlled, multicentre clinical trial investigating the effects of targeted retreatment of COPD exacerbations with antibiotics.

Patients who experience an exacerbation of COPD treated with antibiotics will attend, two weeks after the start of initial treatment, for a screening visit. Patients will be eligible for the study if they have not fully recovered at this visit (either persistent symptoms or a raised C-reactive protein [CRP]) and fulfil diagnostic and spirometric criteria for COPD.

Eligible participants will be treated with 1 week of ciprofloxacin 500mg BD or placebo. Follow-up will be for a further 3 months, and the primary study endpoint will be the time to the next exacerbation.

Trial duration per participant: 90 days

Estimated total trial duration: 2 years

Planned trial sites: Multi-Site

Total number of participants planned: 144

Main inclusion/exclusion criteria (summary; see section 6.1 & 6.2):

Main Inclusion Criteria:

- Diagnosis of COPD confirmed spirometrically at screening
- COPD exacerbation with treatment commenced 14 days prior to study enrolment and treated with 5-14 days of a non-quinolone antibiotic. Exacerbation here will be defined as an episode of symptomatic worsening of COPD that was treated by the patient's attending clinician. Confirmation of

the initial exacerbation diagnosis will be provided from the case notes, referral letter, or directly from the treating clinician, and will be documented in the CRF.

- Age: ≥ 45 years of age at screening.
- Persistent symptoms and/or a $CRP \geq 8$ mg/L when assessed 2 weeks after exacerbation onset
- Able to complete questionnaires for health status and symptoms and keep written diary cards
- Severity of disease: Patients with a measured $FEV_1 < 80\%$ of predicted normal values at 2 weeks post exacerbation
- Able and willing to give signed and dated written informed consent to participate

Main Exclusion Criteria:

- Other clinically predominant chronic respiratory disease.

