8.5 Treatment procedures

- Ciprofloxacin: 500 mg, twice daily for 1 week (oral)
- Placebo: one capsule, twice daily for 1 week.

Patients will commence the study medication on the day of screening (visit 1)

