8.6 Follow-up visits (V2 & V3)

Patients will return to the hospital at 7 (+3) days (V2) and 28 (+/-3) days (V3) after V1 for follow up appointments. The following procedures will be carried out:

- The occurrence of AE/SAE and exacerbations will be checked and recorded.
- Diary cards will be checked and the patients reminded/re-educated on how to fill these in correctly (see section 8.12).
- Changes to concomitant medications will be recorded including start and stop dates of any modified treatments.

- Blood sample for CRP analysis (see section 8.13)
- Serum sample for future laboratory analysis (see section 8.13)
- Spirometry (see 8.12).
- Where spontaneously expectorated, sputum will be collected and subsequently analysed for bacterial load and antibiotic resistance
- CAT symptom questionnaire.
- At V2 (at 7 days) a pill count will be performed and any unused medication collected to check adherence to the IMP.
- Further investigation and treatment may be organised if indicated in the opinion of the study doctor. This will fall outside the usual study procedures but will be fully documented in the CRF.

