12.4 Randomisation methods

Randomisation will be conducted by the research fellow contacting a central randomisation service (Sealed Envelope™) after the patient has provided informed consent and baseline data (Class A method of randomisation).

Patients will be randomised using a 1:1 ratio from a computer-generated permuted block system of variable sizes. Stratification will take place by site and each patient will be randomised to one of the two treatment groups on an individual basis.

Randomisation will further be stratified according to the type of inclusion criteria (persistent symptoms or raised CRP).

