Due to relocation from the Royal Free Hospital to the Royal Brompton Hospital, a more realistic sample size of 138 is now expected. We do not anticipate a change in the expected proportion of exacerbation-free survival at 90 days of 0.45, and we still allow for 5% dropout. This would result in:

- 90% power to detect a HR of 0.39 an increase in survival at 90 days from 0.45 to 0.73;
- 80% power to detect a HR of 0.46 an increase in survival at 90 days from 0.45 to 0.70.

The recruitment period for this trial is estimated to be 18 months, requiring approximately 20 exacerbations per month to be identified across both sites. It is likely that 2/3 of these will come from RFH and 1/3 from UHA.

Statistical Analysis Plan

Timing of Analyses

• Recruitment of the 138 patients began in the London site in July 2014, and should commence shortly at the Liverpool site.

• Data for completed patients should begin to become available in October 2014.

Descriptive analyses

(i) Should include CONSORT diagram describing patient flow with exclusions (including reasons for exclusions) and total numbers randomised to each treatment arm. This will include attendance at each visit and loss to follow-up (including follow-up time).

(ii) Baseline comparability of randomised groups:

- By December 2015 (approximately), recruitment should be completed, at which point tables of summary statistics will be produced. These tables will include (but are not limited to) the following baseline variables; age (continuous), sex, BMI, smoking status, smoking pack year history, centre, bacterial load, CRP (from blood sample), spirometry measurements, exacerbation history (number experienced in previous year) and questionnaire scores for each randomised group.
- Continuous variables will be summarised using the following statistics; n (nonmissing sample size), mean, standard deviation, median, inter-quartile range, maximum and minimum. The number of missing observations will also be reported.
- The frequency and percentages (based on the non-missing sample size) of observed levels will be reported for all categorical measures. The number of missing observations will also be reported.

Primary outcome analysis

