- Changes in respiratory healthcare status, assessed using SGRQ. SGRQ (score between 0 and 100from baseline to day 90 will be modelled as a normally distributed random variable. Linear regression will be used,

- Changes in respiratory healthcare status, assessed using CAT. CAT (score between 0 and 40) from baseline to day 90 will be modelled as a normally distributed random variable. Repeated measures analysis will be used to assess treatment effects over time during the follow-up period.

- Lung function: Changes in FEV1, FEV1 as % predicted, and FEV1/FVC ratio and FVC at day 90 from day 0 will be modelled separately as continuous outcomes and assumed to be normally distributed. Repeated measures analysis will be used to assess treatment effects over time during the follow-up period.

- Change in CRP from study entry to 90 days will be modelled as a normally distributed random variable. Repeated measures analysis will be used to assess treatment effects over time during the follow-up period.

- Resistance patterns (not resistant, resistant) will be analysed using logistic regression.

- The change in (log10) bacterial load from trial beginning to end will be analysed using parametric survival regression(linear regression with censored outcome data). Values below limits of detection will be treated as left censored.

- Adherence as assessed by pill counts. The number of pills taken over total number dispensed will be modelled using logistic. The difference in percent adherence will be assessed between treatment groups.

- Cost-effectiveness will be assessed as part of a future study (WP5)

This study is not powered to test these secondary outcomes – only the primary outcome. As such, analyses of the secondary outcomes will be hypothesis generating only.

Subgroup analyses

Relevant subgroups may be analysed (including patients who gave sputum samples), allowing the incorporation of any important new information and methodological concerns identified between now and the time of writing the analysis plan. However, such analyses should be undertaken before unblinding, and keeping in mind that any analyses will be hypothesis generating only.

Sensitivity analysis

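### The adherence model treats each patient's 14 capsules as independent, so its confidence interval is too narrow and its false-rejection rate is well above 5%

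*Protocol*

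**What the plan says.** Protocol 12.3.3 states that "The number of pills taken over total number dispensed will be modelled using logistic regression (Binomial distribution with logit link"), and then: "The difference in percent adherence will be assessed between treatment groups". The SAP, under Secondary outcomes, has the same response in a sentence that breaks off: "The number of pills taken over total number dispensed will be modelled using logistic". Neither document names a dispersion parameter, random effect, beta-binomial model or robust variance for this outcome.

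The course is two capsules a day for seven days (protocol 8.5: "Placebo: one capsule, twice daily for 1 week", with the same frequency and duration for ciprofloxacin). Capsules are counted once per patient (protocol 8.6: "At V2 (at 7 days) a pill count will be performed"). The patient is the unit of allocation (protocol 12.4: "each patient will be randomised to one of the two treatment groups on an individual basis").

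For adverse events, exacerbations, antibiotic courses and hospital attendances, protocol 12.3.3 allows over-dispersed Poisson or zero-inflated models. The SAP uses negative binomial regression and notes that this reduces to Poisson when there is no over-dispersion. Adherence has no such provision.

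**The concern.** The binomial variance is right only if whether a patient takes one capsule says nothing about whether the same patient takes the next. In a one-week course the opposite is expected. The documents themselves describe how whole runs of doses are lost together: the study drug is stopped when a contraindicated medicine is started (protocol 9.3), after adverse events (protocol 8.15 and the SAP's discontinuation section), and for many reactions in the risk table of protocol 3.4. One decision removes all remaining capsules.

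The information therefore lies in the number of patients, but the model counts capsules. The interval for the difference in percent adherence comes out too narrow, and a difference due to chance can be reported as real. It could then be read as intolerance of ciprofloxacin. It could also be offered as the reason why the intention-to-treat and per-protocol results disagree, a situation that the SAP's Sensitivity analysis section says will be investigated further.

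**Working it through.** The documents give no figure for the adherence analysis, so there is none to reproduce.

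**Inputs from the documents**
- Capsules per patient: m = 2 × 7 = 14.
- Patients: the protocol synopsis has "Total number of participants planned: 144" (72 per arm); the SAP says "a more realistic sample size of 138 is now expected" (69 per arm).
- Test level: none is set for adherence. The two-sided 5% of the primary outcome (protocol 12.2.1) is carried over.

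**Assumptions**
- Within-patient correlation ρ: range 0 to 0.7.
- Mean adherence: 85% to 95%.

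**Step 1: formulas.** The number of capsules Y that a patient takes has variance m·p(1−p)·[1 + (m−1)ρ]. The plan's model uses m·p(1−p). Hence:
- design effect DE = 1 + 13ρ
- true SE ÷ model SE = √DE
- actual two-sided error of a nominal 5% test = 2·[1 − Φ(1.96/√DE)]

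**Step 2: the interval the model reports.** With 69 per arm there are 69 × 14 = 966 capsules per arm. At 90% adherence in both arms the model SE of the difference is √(2 × 0.9 × 0.1/966) = 0.01365. The 95% interval is then ±1.96 × 1.365 = ±2.7 percentage points, whatever ρ is.

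**Step 3: results.** The simulated column is from beta-binomial data with no difference between arms: 10,000 trials per setting, 69 or 72 per arm, mean adherence 85%, 90% or 95%. The last row is from 20,000 trials with 69 per arm and mean adherence 85% to 90%.

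| ρ | DE | SE ratio | Correct half-width (points) | False rejection, formula | False rejection, simulated |
|---|---|---|---|---|---|
| 0 | 1.00 | 1.00 | 2.7 | 5.0% | 4.7–5.3% |
| 0.01 | 1.13 | 1.06 | 2.8 | 6.5% | not run |
| 0.05 | 1.65 | 1.28 | 3.4 | 12.7% | 12.0–13.2% |
| 0.1 | 2.30 | 1.52 | 4.1 | 19.6% | 19.3–19.8% |
| 0.3 | 4.90 | 2.21 | 5.9 | 37.6% | 36.8–38.1% |
| 0.5 | 7.50 | 2.74 | 7.3 | 47.4% | 46.5–48.1% |
| 0.7 | 10.10 | 3.18 | 8.5 | 53.7% | 54% |

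At ρ = 0.5 the 72 × 14 = 1008 capsules per arm carry the information of 1008/7.5 ≈ 134 independent ones.

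**Step 4: a pattern that fixes no ρ.** Suppose a proportion q of patients stop at a random point (0 to 13 capsules taken, equally likely) and the rest take all 14. The number missed has mean 7.5q and variance 72.5q − 56.25q². For q = 0.10:
- true variance = 7.25 − 0.5625 = 6.6875
- mean adherence = 1 − 0.75/14 = 94.6%
- binomial variance = 0.75 × 0.946 = 0.710
- DE = 6.6875/0.710 = 9.4, SE ratio 3.1, false rejection about 52%

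For q = 0.05 and q = 0.20 the same arithmetic gives DE of 9.5 and 9.1, and false rejection of about 53% and 52%. DE of 9.1 to 9.5 corresponds to ρ of about 0.63 to 0.66. If each dose also has a 3% chance of being missed by accident, simulated false rejection is about 37% to 47%.

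**Step 5: after correction.** In the same beta-binomial simulations a quasi-binomial SE rejects in 4.3% to 5.3% of trials and a patient-clustered robust SE in 4.6% to 6.5%. In the stopping patterns the quasi-binomial SE rejects in at most about 6%.

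**The case against.** The best case against concerns the weight of the point rather than the mechanism.

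- **The size rests on an assumed ρ.** This stands. At ρ = 0.01 the error is 6.5%, which would do little harm. A course that is either finished or stopped makes a high ρ likely, but no data in the documents confirm it. Nor do they show that clustering is stronger here than in the other counts, and the argument does not need that.
- **No test or level is named for adherence.** This stands: the documents say only that the difference will be assessed. The false-rejection figures borrow the primary outcome's 5%. The narrow interval does not depend on that choice.
- **The SAP is incomplete rather than wrong.** This is partly true. Its sentence ends without a distribution or a variance estimator; the explicit binomial wording is in the protocol. A default logistic fit to pills taken over pills dispensed gives the same standard error.
- **Little depends on it.** This stands as to severity. Adherence is not in the outcome lists of protocol 4.2 or 12.1.2. Secondary analyses are labelled hypothesis generating. The primary analysis is by intention to treat, the per-protocol set uses full compliance, and tolerability has its own adverse-event outcome. The descriptive summaries promised for secondary endpoints, if produced for adherence, would show the spread between patients.

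The exploratory label excuses low power. It does not excuse an interval that lacks its stated coverage.

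**Conclusion.** The concern holds. As specified, the adherence model ignores within-patient correlation, and its standard error is too small for any positive ρ. For assumed ρ of 0.1 to 0.7 the understatement is a factor of 1.5 to 3.2, with false rejection of about 20% to 54% at a borrowed 5% level. A stop-or-finish pattern gives a factor of about 3 and about 52%. These are error rates when the arms are equal; they do not mean that a false finding is certain. The result rests on 14 capsules per patient, the planned sample sizes and the assumed correlation. Mean adherence between 85% and 95% hardly changes it. The primary and per-protocol analyses do not use this model and are unaffected. The specification should be corrected before the analysis is run, as a fault in a secondary analysis.

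**What to change.** Keep the outcome and the comparison, and make the patient the unit of variance. In the SAP adherence item and in protocol 12.3.3, specify one of these: quasi-binomial logistic regression with estimated dispersion, beta-binomial regression, or binomial logistic regression with patient-level robust (sandwich) standard errors. In the simulations quasi-binomial stayed closest to 5%; the robust version rose to 6.5% at 95% adherence with ρ = 0.5. Complete the SAP sentence at the same time, so that it names the distribution, the link and the variance estimator.

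The cost is one option in the model call and a line of text in each document. It needs no new data, visits or patients. The interval becomes wider, for example about ±5.9 instead of ±2.7 percentage points at 90% adherence and ρ = 0.3.
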